3.2.3 Exclusion Criteria

Subjects presenting with any of the following **will not** be included in the study:

1. Contraindication to triptans
2. Use of any prohibited concomitant medications within 10 days of the Run-in Period (See [Section 6.2.11](#) for list of prohibited concomitant medications prohibited for the duration of the study)
3. Use of any prescription anti-coagulant including Pradaxa (dabigatran), Coumadin (warfarin sodium), Eliquis (apixaban), and/or Xarelto (rivaroxaban) within 30 days prior to screening and throughout the duration of the study.
4. History of hemiplegic migraine or migraine with brain stem aura (formerly called basilar migraine)
5. Participation in another investigational trial during the 30 days prior to the Run-in Period or during this study
6. Diagnosis of cancer (other than non-invasive skin cancer) within the 5 years prior to the Run-in Period
7. History of unstable psychiatric illness requiring medication changes or hospitalization in the 12 months prior to the Run-in Period
8. Known allergy or sensitivity to zolmitriptan or its derivatives or formulations
9. Known allergy or sensitivity to adhesives and/or titanium
10. Planned participation in activities which cause inflammation, irritation, sunburn, lesions, and/or tattoos at the intended application site from two weeks prior to screening through the last day of study participation
11. Use of greater than 5 doses of opioid or barbiturate containing medications in the preceding 30 days prior to screening and/or who anticipate using more than 5 doses per month of these medications at any time during the study
12. Women who are pregnant, breast-feeding or plan a pregnancy during this study
13. Clinically significant liver disease (SGPT > 150 U/L; SGOT > 130 U/L or LDH > 750 U/L)
14. History of coronary artery disease (CAD), coronary vasospasm (including Prinzmetal's angina), aortic aneurysm, peripheral vascular disease or other ischemic diseases (e.g., ischemic bowel syndrome or Raynaud's syndrome)
15. Three or more of the following CAD risk factors identified during screening:

- Current tobacco use
 - Hypertension (systolic BP > 140 or diastolic BP > 90) or receiving anti-hypertensive medication for treatment of hypertension
 - Hyperlipidemia – LDL > 159 mg/dL and/or HDL < 40 mg/dL (or on prescribed anti-cholesterol treatment)
 - Family history of premature coronary artery disease (CAD) (< 55 years of age in male first degree relatives or < 65 years of age in female first degree relatives)
 - Diabetes mellitus
16. History of cerebral vascular accident (CVA), transient ischemic attacks (TIA), or seizures
 17. History of concurrent illness that requires hospitalization within the 30 days prior to the Run-in Period
 18. Any other household member currently participating in a M207 study or relatives of site staff
 19. Any reason to believe that compliance with the study requirements and completion of evaluations required for this study will not be possible
 20. Any language barrier that, in the opinion of the Investigator, would preclude communication or compliance with the study requirements
 21. History or current abuse or dependence on alcohol or drugs that in the opinion of the investigator would interfere with adherence to study requirements
 22. Any positive urine drug screen for phencyclidine (PCP), MDMA (ecstasy), cocaine, and/or methamphetamine(s)
 23. Any clinically relevant abnormal findings in the subject's medical history, physical exam, vital signs or laboratory tests that, in the opinion of the Investigator, may put the subject at risk

3.2.4 Eligibility Criteria for Study Treatment

To be eligible for Treatment, subjects must continue to meet all eligibility criteria for the study and the following criteria observed during the Run-in Period:

1. At least one qualifying migraine attack in the last 14 calendar days prior to Visit 3 (Day1). The following constitutes a migraine that qualifies during the Run-in Period:
 - a) Headache has at least two of the following characteristics:
 - unilateral location
 - pulsating quality
 - moderate or severe pain intensity
 - aggravation by or causing avoidance of routine physical activity (e.g., walking or climbing stairs)
 - b) During headache at least one of the following:
 - nausea and/or vomiting
 - both photophobia and phonophobia
2. No more than seven headache days (headache days include both qualifying migraines and/or other headache types) in the last 14 calendar days prior to Visit 3 (Day 1)
3. During the run-in period, good eDiary compliance will be confirmed by subject completion of at least 10 out of the 14 calendar days prior to Visit 3 (Day 1)
4. Demonstrated ability to properly operate the eDiary
5. Demonstrated ability to properly apply the demo study drug patches
6. In the opinion of the investigator, subject is willing and able to treat all eDiary-confirmed migraines for up to 12 months with good eDiary completion compliance
7. Confirmation of continuing good general health, or stable non-serious disease that in the opinion of the Investigator will not place the subject at risk

3.2.5 Prior and Concomitant Medications Allowed During the Study

Medications that are considered necessary for the subject's welfare and are not specifically prohibited ([Section 6.2.11](#)), may be given at the discretion of the investigator. All medication(s) taken within 30 days prior to the screening visit and throughout the study must be recorded in the appropriate source document and in the case report form (CRF). Over the counter medications, topical skin ointments and/or creams, prescription medications, herbal supplements and/or vitamins will be recorded as concomitant medications.

Migraine prophylaxis medications are allowed if subjects have been on a stable dose for at least 30 days prior to screening and with no changes during the study.

Medications with ergot or another triptan or vasoconstrictor drugs are prohibited on the day of a confirmed migraine prior to M207 application and for 24-hours post-administration of M207.

Aspirin, acetaminophen, NSAIDS and other PRN or daily medications indicated specifically for migraine symptoms are prohibited on the day of a confirmed migraine prior to M207 application and during the two hours following M207 application.

Following M207 application, subjects will enter into the eDiary whether they took any medications (other than M207) for migraine symptoms prior to M207 application (on the day of application) or during the 48 hours post M207 application.

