6.1.3 Day 1 (Visit 3, Dispense Study Medication)

- Perform brief physical exam, including weight
- Record vital signs: temperature, respiratory rate (RR), blood pressure (BP), and heart rate (HR)
- Review run-in eDiary data for subject compliance and eligibility for treatment
- Confirm subject is willing to treat all eDiary-confirmed migraine attacks with study medication, and is willing to consistently perform eDiary completion for up to 12 months
- Record concomitant medications, including medication(s) taken to treat migraine attacks
- Urine pregnancy test for all WOCBP
- Record Adverse events
- Train the subject on how to apply the patch to the upper arm with the applicator and have the subject practice applying the demo patches to his/her arm 2-3 times (more is allowable, if necessary)
- Record that the subject can apply patch(es) with the applicator unaided
- Instruct the subject to apply the patches on the same upper arm for each application
- Reconfirm subject's eligibility based on inclusion/exclusion criteria
- Dispense CTM kit and the applicator
- Provide instructions for scheduling the next visit in one month

- Remind the subject that ergot, another triptan and/or vasoconstrictor drugs are prohibited on the day of patch application prior to applying and within 24-hours post-administration of the patch
- Provide any follow-up eDiary training necessary and re-dispense the eDiary
- Dispense the Subject Skin Grading Card (Appendix 4) and instruct the subject to refer to this card when grading their skin reaction(s)/symptom(s) in the eDiary.

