6.1.4 Treatment Phase: Up to 12 Months

Visit 3 will be considered the “Day 1” visit for data capture purposes. Subjects will be instructed to complete the eDiary at the time of each suspected migraine attack. Once the eDiary confirms that the migraine qualifies for treatment, the subject will follow the steps provided to self-administer the study drug. If necessary, subjects may return for unscheduled visits for dispensation of additional drug kits.

The following constitutes a migraine that qualifies for treatment with study drug:

- No medication has already been taken to treat the migraine symptoms on the day of the suspected attack before applying M207.
- Presence of at least two of the following characteristics:
 - Unilateral location
 - Pulsating quality
 - Moderate or severe pain intensity
 - Aggravation by or causing avoidance of routine physical activity (e.g., walking or climbing stairs)
- During headache, at least one of the following:
 - Nausea and/or vomiting
 - BOTH photophobia AND phonophobia

The following procedures are to be started at Day 1 after receiving study medication:

- Using the eDiary, the subject will record the following to confirm the headache meets the qualifications for a migraine:
 - Migraine symptoms and pain assessment
- Once the qualifying migraine has been confirmed, subject self-administers the study drug patches. Patches cannot be applied to a previous application site unless the site is free of redness, swelling, and/or bruising. In addition, patches must not be applied to any area where the skin appears tattooed, sunburned, broken and/or irritated.
- Each set of two patches must be applied next to one another (or one above the other), on the same arm. If any skin appears broken or irritated, subsequent doses will be applied a few inches away from the previously applied patches on the same arm (or both patches on the other arm) to avoid applying in an irritated area.
- Qualifying migraine attacks cannot be treated any earlier than 48 hours after the time of patches application for a previously treated migraine attack.
- Subject will continue to record the following in the eDiary at specified time points as follows:
 - Migraine symptoms and pain assessment at the time of treatment, 30 minutes, 2 hour, 12 hours, 24 hours, and 48 hours post patch application
 - Subject reported skin assessment for bleeding at 30 minutes only

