6.2.11 Concomitant and Prohibited Medications

Concomitant medications, taken within 30 days of screening and throughout the study, include over the counter medications, topical skin ointments and/or creams, prescription medications, herbal supplements, and/or vitamins. These medications will be recorded on the appropriate source document and on the appropriate CRF at all visits including screening, run-in, and end of study (or early discontinuation) through the duration of the study.

Migraine prophylaxis medications are allowed if subjects have been on a stable dose for at least 30 days prior to screening and with no changes during the study.

Medications with ergot or another Triptan or vasoconstrictor drugs are prohibited on the day of the confirmed migraine prior to M207 application and for 24-hours post-administration of M207.

Aspirin, acetaminophen, NSAIDS, and other PRN or daily medications taken specifically for migraine symptoms are prohibited on the day of a confirmed migraine prior to M207 application and during the two hours following patch application.

On the day of M207 application, subjects will enter into the eDiary whether they took any medications (other than M207) for migraine symptoms prior to M207 application and/or during the 48 hours post M207 application.

Table 12 lists all prohibited concomitant medications taken within 10 days prior to the Run-in Period and for the duration of this study.

Table 12: Prohibited Concomitant Medications

Drug Type	Medication
Monoamine oxidase inhibitors	Selegiline Tranlycypromine Isocarboxazid phenelzine
Selective serotonin reuptake inhibitors (SSRIs)	Paroxetine Fluoxetine Sertraline Citalopram Escitalopram Fluvoxamine
Serotonin-norepinephrine reuptake inhibitors (SNRIs)	Duloxetine Venlafaxine Desvenlafaxine Milnacipran Levomilnacipran
All Prescription Anticoagulants	Pradaxa Coumadin Eliquis Xarelto

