APPENDIX 3 – eDiary Questions

Most Bothersome Symptom (To be completed when site is setting up the eDiary for the subject)

- Ask the subject what his/her most bothersome symptom is. This is the symptom other than pain that is most bothersome most of the time with their migraine. (Sick to their stomach, sensitive to light, sensitive to sound/noise)

Run-in Period Diary, Nightly Questions (Start the evening of Visit 2)

- Did you have a headache in the past 24 hours? (Yes, No)
- *If No is answered for bullet one question*
 - Did you experience excessive yawning today? (Yes, No)
 - Did you experience mood changes today? (Yes, No)
 - Did you experience excessive fatigue (tiredness) today? (Yes, No)
- *If yes, please answer the following questions based on your headache symptoms in the last 24 hours:*
 - How bad was your headache pain at its worst? (Mild, Moderate, Severe)
 - Was the headache pain on only one side of your head? (Yes, No)
 - Was the headache pulsating (throbbing)? (Yes, No)
 - Did activity make your headache get worse? (Yes, No)
 - Were you nauseated (sick to your stomach)? (Yes, No)
 - Did you vomit (throw up)? (Yes, No)
 - Did light bother you? (Yes, No)
 - Did sound or noise bother you? (Yes, No)
 - Did you take any medication to treat your headache? (Yes, No)

Migraine Treatment Diary (Starts at Day 1 when subject feels he/she is experiencing a migraine attack)

Please fill in your diary when you feel you are experiencing a migraine attack

- Are you currently experiencing a migraine attack? (Yes, No)
- How bad is your headache pain? (Mild, Moderate, Severe)
- Is the headache pain on only one side of your head? (Yes, No)
- Is the headache pulsating (throbbing)? (Yes, No)
- Does activity make your headache pain get worse? (Yes, No)
- Are you nauseated (sick to your stomach)? (Yes, No)
- Did you vomit (throw up)? (Yes, No)
- Does light bother you? (Yes, No)
- Does sound or noise bother you? (Yes, No)
- Have you taken any medication to treat your headache? (Yes, No)
- Were you experiencing an aura (e.g., flickering light, flashes, or spots) at the start of headache? (Yes, No)
- What day and time did your headache start? (Today, Yesterday) Choose time
- Did you wake up with this headache? (Yes, No)
- eDiary confirms whether this is a qualified migraine and instructs subject to apply the patches:
- *If a non-qualifying migraine:*

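### Other triptans, ergots and vasoconstrictors are barred for 24 hours after M207 but only on the same calendar day before it, so a compliant subject can apply M207 within 24 hours of another triptan taken for a different headache

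*Protocol*

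**What the plan says.** - **The rule.** Protocol 3.2.5 says that ergots, other triptans or "vasoconstrictor drugs are prohibited on the day of a confirmed migraine prior to M207 application and for 24-hours post-administration of M207". Section 6.2.11 repeats it ("prohibited on the day of the confirmed migraine prior to M207 application and for 24-hours post-administration of M207"), and SAP 7.5.1 copies that sentence. The Day 1 reminder to the subject in 6.1.3 has the same shape: "prohibited on the day of patch application prior to applying and within 24-hours post-administration of the patch".
- **The condition for dosing.** Section 6.1.4 requires: "No medication has already been taken to treat the migraine symptoms on the day of the suspected attack before applying M207". The Migraine Treatment Diary in Appendix 3 puts this to the subject as "Have you taken any medication to treat your headache? (Yes, No)".
- **The interval between M207 doses.** Section 6.1.4: "Qualifying migraine attacks cannot be treated any earlier than 48 hours after the time of patches application for a previously treated migraine attack".
- **Recording.** Section 3.2.5: "All medication(s) taken within 30 days prior to the screening visit and throughout the study must be recorded in the appropriate source document"; the CRF is named as well. The eDiary also asks about other medication "for migraine symptoms prior to M207 application (on the day of application) or during the 48 hours post M207 application".
- **The study-long prohibited list.** Table 12 in 6.2.11 covers monoamine oxidase inhibitors, SSRIs, SNRIs and prescription anticoagulants. It has no row for triptans or ergots.

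**The concern.** The same sentence uses a day for the time before M207 and 24 hours for the time after it. Neither document defines the day otherwise, so the natural reading is the calendar day. The separation before a dose then depends on the clock: a triptan at 22:00 rules out M207 at 23:00 but not at 06:00 the next morning.

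The primary objective is the long-term safety of repeated M207 use. The protocol sets 24 hours between M207 and a later triptan. In the reverse order, a fully compliant subject can receive the two drugs closer together than that, and no stated reason explains the difference.

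**Working it through.** The plan gives no figure to reproduce, so the check is clock arithmetic, then a reading of the other rules, then an illustrative frequency.

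**1. Time left uncovered.** If M207 is applied at clock hour h, a same-day bar covers the h hours before it and leaves 24 − h hours of a 24-hour window uncovered.

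| M207 applied at | Covered | Uncovered |
|---|---|---|
| 06:00 | 6 h | 18 h |
| 08:00 | 8 h | 16 h |
| 12:00 | 12 h | 12 h |
| 18:00 | 18 h | 6 h |

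The gap after a triptan at hour t the previous day is (24 − t) + h. For t = 22 and h = 6, 8 or 12, it is 8, 10 or 14 hours.

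**2. Two compliant routes.** The first uses the window in which another triptan is allowed again (from 24 h) but M207 is not (before 48 h):

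| Time | Event | Hours from first M207 | Why allowed |
|---|---|---|---|
| Monday 08:00 | M207, first attack | 0 | qualifying migraine |
| Tuesday 20:00 | other triptan, second attack | 36 | past the 24 h bar; M207 still locked out |
| Wednesday 16:00 | M207, third attack | 56 | past 48 h; no triptan that day; this headache untreated |

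The gap is 56 − 36 = 20 h. With the triptan at 38 h (Tuesday 22:00) and M207 at 48 h (Wednesday 08:00), it is 10 h.

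The second route is a headache that the eDiary rejects as non-qualifying. The subject may not apply patches, may take another triptan in the evening (provided any earlier M207 dose is more than 24 h past), and may have a new qualifying migraine next morning. On the text alone the gap could be minutes across midnight, though two distinct headaches that close are unlikely.

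**3. Whether another rule closes the gap.**
- Table 12 does not list these drugs.
- Contraindication to triptans (3.2.3) is an entry criterion, not a check at each attack.
- The 6.1.4 condition and the eDiary item concern treatment of the present attack. A truthful subject answers No about a triptan taken for a different headache.
- The 48-hour rule runs only from a previous M207 application.

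**4. Illustrative frequency, first route only.** Inputs from the documents are 2–8 attacks a month, 336 days, and attacks lasting 4–72 h if untreated or unsuccessfully treated. Assumed inputs are:
- Poisson attack onsets between 06:00 and 23:00, with no new onset during an attack;
- an attack duration of zero, 4–24 h or 4–72 h (uniform);
- a probability q that an attack 24–48 h after M207 is treated with another triptan.

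There were 30,000 simulated subjects per setting. Results at 4 attacks a month:

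| Duration | Doses <24 h after other triptan, q = 0.25 / 1 | Subjects with at least one, q = 0.25 / 1 |
|---|---|---|
| 4–72 h | 0.013% / 0.059% | 0.5% / 2.0% |
| 4–24 h | 0.104% / 0.415% | 3.6% / 13.5% |
| zero (upper case) | 0.141% / 0.542% | 4.9% / 17.3% |

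The documents give no floor for q. At q = 0 the share is zero by construction; at q = 0.05 with 4–24 h attacks it is about 0.02% of doses and 0.8% of subjects. At 8 attacks a month, 4–24 h and q = 1, it is 1.47% of doses.

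The median gap was 20–22 h, a shortfall of 2–4 h from 24.

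For the whole trial at 4 a month, 4–24 h and q = 1, there would be about 37 such doses if all 250 subjects stayed 336 days (250 × 336 = 84,000 subject-days). At the retention floor (50 × 336 + 100 × 168 = 33,600 subject-days) there would be about 37 × 33,600 / 84,000 = 15. The second route would add to these and is not quantified.

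**The case against.** The strongest reply is that the rule is stated consistently everywhere, so there is no contradiction, and that no section asks for 24 hours before M207. This stands: the symmetric standard is an inference from the post-dose rule. A reader might infer that the plan permits doses known to be unsafe; the documents do not support that, because they show no equal risk in the reverse order.

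The other controls are real but do not stop the dose:
- Other medication is at the investigator's discretion, but nothing triggers a review before each patch.
- Subjects must be willing to treat all confirmed migraines with M207, but on both routes M207 is unavailable when the triptan is taken.
- The eDiary item has no look-back limit, so it blocks any headache already treated, even one that began the day before. A reader might infer that the same attack can be treated twice; it cannot.
- SAP 8.1.7 counts pain or rescue medication up to 48 h as recurrence if the attack was pain-free at 2 h. That is an analysis definition, not a dosing rule.

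A reader might also infer that the overlap goes unseen. It does not. All medication goes into the CRF, and on the first route the previous dose's diary asks about other medication up to 48 h, though only as Yes or No, without drug or time.

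The objection to the percentages also stands. Neither document says that subjects hold another triptan, and simple analgesics are allowed from 2 h after M207, so q near zero is compatible with the plan. Finally, no interval is set between two non-study triptans, so a subject refused M207 might take a second one. The change would control the spacing of M207 only.

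**Conclusion.** The point holds as a minor design weakness. The wording before and after the dose is asymmetric in all four places, and no other rule prevents M207 within 24 hours of another triptan taken the previous day for a different headache. It rests on reading the day as the calendar day and on taking the protocol's own 24 hours as the relevant interval in both directions.

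The event is likely uncommon, and most modelled gaps fall only a few hours short of 24. The simulated figures show a possible order of size and are not estimates for this trial. No bias in any safety or efficacy endpoint is claimed, and nothing in the documents would support such a claim.

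**What to change.** 1. In Protocol 3.2.5, 6.1.3 and 6.2.11 and in SAP 7.5.1, change the pre-dose wording for ergots, other triptans and vasoconstrictors to *within 24 hours before M207 application*.
2. In 6.1.4, add this as a dosing restriction beside the 48-hour rule, not to the definition of a qualifying migraine. A blocked attack then still counts towards the six qualifying migraines in 12 weeks in the withdrawal reasons (3.2.6.1).
3. Add one Migraine Treatment Diary item: *In the past 24 hours, have you taken another triptan, an ergot, or a medicine on your vasoconstrictor list, for any reason? (Yes, No)*. Give the subject a short list, because the protocol does not define the term. Yes should lead to a do-not-apply message that does not call the migraine non-qualifying. Leave the existing same-headache item unchanged.

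The cost is three protocol sentences, one added restriction, one SAP sentence, one eDiary item with its message, and a short list. A small number of attacks would go untreated with M207, which slightly lowers the treated-migraines-per-month compliance measure in SAP 11.1. In the same illustrative model at 4 attacks a month (first route, q = 0.25 to 1), the rule blocks 0.016–0.067% of doses for 4–72 h attacks, 0.099–0.400% for 4–24 h and 0.143–0.554% at zero duration. Mistaken Yes answers would add to this; the list should keep them few.
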